### 9.2 Populations for Analysis

#### 9.2.1 Intent-to-Treat Population

The ITT population is defined as all subjects enrolled into the study. Subject disposition will be based on the ITT population.

#### 9.2.2 Safety Population

All subjects who receive at least one partial dose of study drug will be included in the safety dataset for analysis (SAF) population. Subjects will be analyzed according to the treatment they actually received. The safety population will be used for the safety analyses.

### 9.3 Subject Disposition

Study completion data will be summarized for all enrolled subjects. The number and percent of subjects who complete treatment; discontinue study procedures prematurely; or discontinue the

study prematurely will be tabulated. The primary reason for premature discontinuation of the experimental administration of study drug and/or discontinuation from study participation will be tabulated. Any additional reason(s) for premature discontinuation of experimental study drug administration will also be tabulated. A listing of all enrolled subjects will be provided.

## **9.4 Demographics and Baseline Characteristics**

Descriptive statistics will be presented for demographic and other baseline characteristics for the ITT population. Medical history and medication history findings will be listed and summarized.

## **9.5 Safety Analyses**

The safety analyses will include descriptions of treatment-emergent AEs, Class C events per the CDC Classification System for HIV Infection, clinical laboratory test results, physical examination findings, vital sign results, and Trogarzo® antibody levels (immunogenicity of Trogarzo®).

### **9.5.1 Adverse Events**

The incidence (n and %) of AEs, SAEs, and early termination of experimental study drug administration or study participation due to an AE will be presented. Additionally, AEs will be tabulated according to severity and relatedness categories as reported by the investigator. AEs will be presented in tables organized alphabetically by Preferred Term within SOC. Each subject will be counted only once for each AE reporting level.

### **9.5.2 Clinical Safety Laboratory Parameters**

Clinical laboratory parameters will be presented by visit. Descriptive statistics will be used to summarize observed values by visit as well as the change from baseline at each visit. Clinical laboratory values outside the normal ranges will be flagged in subject data listings. Non-numeric data will be presented in subject data listings but will not be tabulated.

## 9.6 Efficacy

Assessment of the HIV-1 viral loads will be made as a secondary endpoint in HIV-1 infected subjects by comparing the mean viral load at visits when subjects received an IVI over 15 minutes to the weekly visits when receiving an IV push over 30 seconds or IM injections.

Study subjects will be considered virologic failures if:

1. Viremic subjects experience a sustained  $>0.5$  log increase in plasma HIV-1 RNA from baseline  
or
2. A sustained viral load (VL)  $>200$  copies/mL if subject VL was  $<50$  copies/mL at baseline

that cannot be explained by intercurrent illness, a change in adherence to the background regimen, or unanticipated changes to the background regimen that will meet the definition of virologic failure.

Sustained is defined as 2 consecutive viral load determinations at least 2 weeks apart.

Exploratory statistical analyses will explore changes in HIV-1 drug sensitivity/susceptibility to determine relationships with Trogarzo® administration in combination with background ARVs.

## 9.7 Pharmacokinetic Analyses

Serum concentrations will be used to estimate PK parameters. PK parameters will be estimated for all subjects by noncompartmental analysis of the serum concentration-time data. Missing data will not be imputed. For the re-enrolled participants, the PK parameters of IVI and IM will be estimated from their first enrollment and second enrollment, respectively. The exposure-response relationship established for the review of the ibalizumab Biologics License Application (BLA) was based on  $C_{trough}$ , rather than AUC.  $C_{trough}$  was used as an indicator of exposure and a clear trend between exposure and the efficacy endpoint was observed. Therefore,  $C_{trough}$  is more representative of efficacy for this pharmacokinetic bridging study than AUC. A PK bridge between the IV push and IVI and between the IM injection and IVI is demonstrated if the proportions of subjects with average  $C_{trough}$  equal to or exceeding the threshold of 300 ng/mL are comparable using a Fisher's Exact test. A PK bridge is also demonstrated for AUC if the 90% confidence interval of log transform of the ratio of the geometric means for IV push or IM injection (test product) to IVI (reference product) for the 40 subjects in the study is within the 80%-125% criteria.

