	
was used as an indicator of exposure and a clear trend between exposure and the efficacy endpoint was observed. Therefore, <math>C_{trough}</math> is more representative of efficacy for this pharmacokinetic bridging study than AUC. A PK bridge between the IV push and IVI and between the IM injection and IVI is demonstrated if the proportions of subjects with average <math>C_{trough}</math> equal to or exceeding the threshold of 300 ng/mL are comparable using a Fisher's Exact test. A PK bridge is also demonstrated for AUC if the 90% confidence interval of log transform of the ratio of the geometric means for IV push or IM injection (test product) to IVI (reference product) for the 40 subjects in the study is within an 80%-125% criteria.
 
Secondary Endpoint Analysis: Assessment of the HIV-1 viral load measurements will be made as a secondary endpoint in HIV infected subjects by comparing the mean viral load at visits when subjects received an IV infusion to the visits when receiving an IV push over 30 seconds or receiving IM injections.
 
HIV-infected study subjects will be considered virologic failures if:
 

1. Viremic subjects experience a sustained <math>>0.5</math> log increase in plasma HIV-1 RNA from baseline or

2. A sustained <math>VL > 200</math> copies/mL if subject VL was <math>< 50</math> copies/mL at baseline

 
that cannot be explained by intercurrent illness, a change in adherence to the background regimen, or unanticipated changes to the background regimen will meet the definition of virologic failure. Sustained is defined as 2 consecutive viral load determinations at least 2 weeks apart.
 
Exploratory statistical analyses will examine any noted changes in HIV-1 drug sensitivity/susceptibility in participants with an increase in plasma viral load to levels above 1,000 copies/mL on 2 consecutive measurements at least 2 weeks apart.

Pharmacokinetics (PK)	
PK Analysis: PK samples will be collected during the study as shown in the Schedule of Events. These samples will be collected from subjects at selected times to evaluate PK parameters.

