#### **4.5. PK**

The PK endpoints are to compare the trough serum drug concentration and AUC after IV Infusion with the diluted drug to the trough concentration and AUC after IM injection with the undiluted drug. Serum concentrations will be used to estimate PK parameters. PK parameters will be estimated for all subjects by non-compartmental analysis of the serum concentration-time data. Missing data will not be imputed. The trough concentrations and AUC for IM injection and IV infusions over 15 minutes will be

estimated. The following graphic illustrates the time points at which the  $C_{trough}$  and AUC values will be estimated.

The  $C_{trough}$  values for all IM injection and all IV infusions over 15 minutes will be estimated. A PK bridge will be demonstrated if the proportion of subjects with mean  $C_{trough}$  equal to or exceeding the threshold of 300 ng/mL are comparable for IV infusion over 15 minutes to IM injection. Both the geometric and arithmetic mean  $C_{trough}$  will be calculated and analysis results will be presented for both means. Analysis will be conducted by pooling all the  $C_{trough}$  measurements into two groups (IVI=Reference; IMTest) and dichotomizing the  $C_{trough}$  data ( $< 300$  ng/mL=1;  $\geq 300$  ng/mL=0). Fisher's exact test for comparing two independent binomial proportions will be conducted initially to test for equality of the proportions. In a subsequent test, the PK bridge will be based on relative risk assuming that the binary data in the two infusion groups are independent samples. Two one-sided tests of significance (TOST) will be carried out for the pair of hypotheses,  $H_{0a}: \rho \leq \rho_0$  versus  $H_{1a}: \rho > \rho_0$  and  $H_{0b}: \rho \geq \rho_1$  versus  $H_{1b}: \rho < \rho_1$ . Rejection of both  $H_{0a}$  and  $H_{0b}$  would mean that the relative risk lies in the zone of equivalence. The syntax below will be used in SAS to carry out the score test with  $\rho_0 = 0.8$ , and  $\rho_1 = 1.25$ .

```
proc freq data=<filename> order=data;
tables group*Cthrough/relrisk(equivalence margin=(.80, 1.25)
method=FM);
weight count;
format Cthrough Cthrough.;
run;
```

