Details of reported outputs from the analysis will be displayed in the mock tables and will include relative risk, equivalence limits, 90% confidence limits, and TOST p-values of lower margin, upper margin, and overall. Missing data will not be imputed or used in the analysis. In addition, the two-tailed p-value from Fisher's exact test will be presented to provide additional supporting evidence for equality of binomial proportions between the two administrative routes in the Ctrough cutoff at 300 ng/mL.

A 90% confidence interval of log transform of the ratio of the geometric means for IM injection to IV infusion will be calculated. Additionally, the PK bridge between the IM injection and IV infusion is demonstrated for AUC if the 90% confidence interval of log transform of the ratio of the geometric means for IM injection (test product) to IV infusion (reference product) for the 20 subjects in the study is within a 80%-125% criteria.

In accordance with the FDA Guidance (2001) [2], SAS PROC MIXED will be used to fit a factor-analytic variance-covariance structure using the FA0(2) option to the ln-transformed AUC data by subject, group (HIV+ or HIV-), PK period, and infusion type (IVI=Reference; IM=Test) to estimate 80%-125% criteria. For each type of administration, subject-level AUC data will be labeled as PK Period 1 or PK Period 2 corresponding to the graphic above. Unless a subject has missing data for both administration routes and both periods, the subject's data will be included in the analysis because SAS PROC MIXED can handle missing data. Details of reported outputs from the analysis will be displayed in the mock tables and will include mean estimate and its lower and upper bounds.

The following SAS code syntax will be used to calculate estimates:

```
proc mixed data=lnauc method=reml;
  class infusiontype population period ;
  model lnauc= population period infusiontype/ddf=kenwardroger;
  random infusiontype /type=FA0(2) subject=subject;
  repeated/group=infusiontype subject=subject;
  estimate 'T-R' infusiontype 1 -1/CL alpha=0.1;
  ods output estimates=test;
  data test;
  set test;
  meanrat= exp (estimate); * Estimated mean ratio on original scale;
  lowerb=exp(lower); * Lower bound on original scale;
  upperb=exp(upper); * Upper bound on original scale;
  proc print data=test noobs;
  var meanrat lowerb upperb;
  run;
```

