## Addendum

Protocol v7.0 (Amendment 6) for the TMB-302 study includes the following update that affects the analysis of the data:

Note: HIV-infected subjects who are enrolled in the IM injection study and are unable to adhere to the study schedule for IM dosing due to factors outside the study will be discontinued. Re-enrollment of HIV-infected IM Group subjects will be allowed after a Discontinuation Visit and Screening Visit are completed provided that inclusion/exclusion criteria continue to be satisfied and dosing after discontinuation is resumed according to the Trogarzo® Prescribing Information. For re-enrolling subjects, the inclusion criteria for stable a Trogarzo®-containing ARV regimen is satisfied with a loading dose of 2000mg IVI and at least one maintenance dose of 800mg IVI given according to Trogarzo® labeling prior to Day 1 enrollment. (Section 3.1 Overall Design)

Additionally with regard to data collection, Protocol v7.0 states:

PK visits between Baseline and Day 29 will not be required for HIV-infected subjects participating in the IM portion of TMB-302 who have re-enrolled after receiving a 2000mg loading dose and one 800 mg dose of Trogarzo® by IVI prior to study re-enrollment since these PK samples will already have been collected during initial study participation. (Table 1 Schedule of Events for IM Group (HIV-Infected and HIV-Uninfected Subjects)

For the purposes of analysis:

1. Subjects who re-enroll will be assigned a new subject ID, and all data will be collected where possible during the second enrollment, with the exception of PK as described above.
2. While all collected data will be submitted for review as part of the CDISC data package:
  - a. PK data for re-enrolled subjects will be combined such that data collected on Day 1 – Day 29 from the first enrollment and data collected after Day 29 from the second enrollment provide one linear set of results with no overlapping. No data collected after Day 29 from the first enrollment will be included in the analyses of the re-enrolled subjects.
  - b. For all data other than PK, only data collected during the second enrollment will be presented in the analyses.

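### The protocol declares the primary trough bridge by a Fisher test with no margin, while both SAPs base it on a relative-risk equivalence test; the two rules can give opposite answers, and the unit of analysis is stated inconsistently

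*Protocol*

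**What the plan says.** Comparing troughs after infusion (IVI) with troughs after IV push or IM injection is a primary objective for both routes (Protocol 2.1). Protocol 9.7 adds that Ctrough represents efficacy better than AUC does. Its rule takes a bridge as shown when the shares of subjects with a mean trough "equal to or exceeding the threshold of 300 ng/mL are comparable using a Fisher's Exact test". The Synopsis has the same rule ("are comparable using a Fisher's Exact test"). Neither place gives a significance level, a margin or a definition of comparable. For AUC, the same section uses an equivalence criterion: a 90% interval within 80%-125%.

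IM SAP 4.5 opens with a subject-level criterion: "A PK bridge will be demonstrated if the proportion of subjects with mean" Ctrough at or above 300 ng/mL is comparable for the two routes. Fisher is run first. The SAP then states: "In a subsequent test, the PK bridge will be based on relative risk", using a Farrington-Manning TOST with limits 0.80 and 1.25. It gives Fisher a supporting role: "the two-tailed p-value from Fisher's exact test will be presented to provide additional supporting evidence for equality of binomial proportions". IV push SAP 4.4 has the same structure and the same ranking of the tests.

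Between criterion and test, each SAP has a method sentence that begins "Analysis will be conducted by pooling all the" trough measurements into two groups. The mock tables of both SAPs report proportions of subjects. The IM SAP computes arithmetic and geometric means, and "analysis results will be presented for both means"; it does not say which one decides. Both SAPs code values below 300 as 1, while the mock tables show the category at or above 300.

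The IM SAP Addendum for protocol v7.0 says that version "includes the following update that affects the analysis of the data", and then deals only with re-enrolment.

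**The concern.** Fisher's test asks whether there is evidence that two proportions differ. With 20 subjects per route it has little power, so a non-significant result is compatible with a large loss of subjects above the threshold. A rule that declares a bridge on that result rewards a small sample. The SAPs' TOST puts the burden of proof the right way round. A reader who holds the protocol and a reader who holds the SAPs could therefore draw opposite conclusions on a primary objective from the same data. Nothing in the documents shown tells them which conclusion stands.

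The pooling sentence adds a second ambiguity. Counting every trough enlarges the denominators and treats repeated values from one subject as independent, so the same observed proportions look more precise than they are.

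**Working it through.** **Plan's own figure.** Protocol 9.8 says 20 subjects per administration gives 80% power. It names no endpoint, test, alpha or true ratio. Its inputs are about 70% variability in clearance (CL) and within-subject AUC CVs of 7% (median) and 22%-23% (maximum). I tried a paired AUC TOST at 80%-125%, n=20, one-sided 0.05, one interval per route, with within-subject log variance ln(1+CV²). Power at true ratio 1.0 is 1.00 (CV 7%), 0.86 (22%) and 0.82 (23%). At ratio 0.95 it is 0.76 and 0.73 for the last two CVs. Using 70% as the CV gives less than 0.001. The claim is plausible for AUC from the within-subject CVs. Nothing in 9.8 bears on the Ctrough criterion.

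**Inputs for the comparison.** n=20 per route (Protocol 9.8); margins 0.80 and 1.25 (both SAPs); one-sided 0.05 on each side (inferred from the SAPs' 90% limits); Fisher two-sided 0.05 (my assumption). The two routes are treated as independent, as the SAPs do.

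**One outcome by hand: infusion 20/20, test 16/20.**
- Fisher: four subjects are below threshold, all on the test route. The probability is C(20,4)/C(40,4) = 4845/91390 = 0.053. The mirror table is equally likely, so the two-sided p = 0.106.
- TOST, lower side: z = (p_test − 0.80 × p_IVI)/SE, with SE from the fit constrained to ratio 0.80. The numerator is 0.80 − 0.80 × 1.00 = 0, so z = 0 and p = 0.50.

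**More outcomes at 20 v 20.**

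| IVI ≥300 | Test ≥300 | Fisher p | TOST lower p |
|---|---|---|---|
| 20 | 16 | 0.106 | 0.50 |
| 19 | 14 | 0.091 | 0.71 |
| 18 | 12 | 0.065 | 0.84 |
| 16 | 10 | 0.096 | 0.85 |

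Of the 21 × 21 = 441 possible tables, Fisher is non-significant in 227 and the TOST passes 5: (test, IVI) = 18/18, 19/19, 19/20, 20/19 and 20/20. All 5 are among the 227, so the rules disagree in 222, always with Fisher non-significant and the TOST failing.

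**Operating characteristics.** The probability of passing is the sum over tables of Bin(x; 20, p_test) × Bin(y; 20, p_IVI) × (1 if the rule passes).

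| True IVI, test | Fisher non-significant | TOST passes |
|---|---|---|
| 90%, 72% (ratio 0.80) | 0.800 | 0.016 |
| 95%, 76% (ratio 0.80) | 0.729 | 0.037 |
| 80%, 63% (ratio 0.79) | 0.857 | 0.001 |
| 95%, 95% | 0.998 | 0.577 |
| 90%, 90% | 0.988 | 0.235 |

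The third row is illustrative. Protocol 1.3 reports 63% of subjects' troughs above 0.3 µg/mL after 800 mg IM in an earlier study. It also reports roughly 20% of subjects below effective levels at Week 2 after an infused loading dose. These are different studies and settings.

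**Unit.** The graphic of trough time points is not shown, so pooled counts are assumed: 2 infusion and 4 IM doses × 20 subjects give 40 v 80, with 40 v 40 as a low case. IVI 19/20 v IM 18/20 fails by subject (lower p=0.078). The same proportions counted as 38/40 v 72/80 pass (p=0.003). With identical routes, subject-level v pooled pass rates are 58% v 97% (91% at 40 v 40) at a true 95%, and 23% v 85% (66%) at 90%. At 90% v 72%, the pooled 40 v 80 TOST passes 5% under independence, and 7% to 10% with an assumed within-subject latent correlation of 0.7 to 0.95.

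**Response category.** If the relative risk were taken on the below-300 category at 20 v 20, the only passing tables would have 0 to 2 subjects of 20 at or above 300 on each route.

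**The case against.** The strongest reply is that the SAPs already solve the problem. They repeat the protocol's criterion, give it a margin, a method and code, and rank Fisher as supporting. If they are followed, no claim rests on Fisher alone, and this is protocol wording that lags behind a stricter analysis plan. The ranking is real. A reader might infer that the sponsor intends to claim the bridge on Fisher, and the SAPs do not support that. Even so, the protocol names Fisher as what demonstrates the bridge, and no text says the SAP rule replaces it.

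Second, the protocol never says that non-significant means comparable, and 9.1 calls the analysis primarily descriptive. That is correct: the Fisher pass rates quantify an inferred rule at an assumed 0.05. But without a margin, no reading of an equality test establishes comparability.

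Third, the IM SAP was written for protocol v6.2 and the IV push SAP for a protocol dated 15 Oct 2020. Those versions are not shown, so the origin of the mismatch cannot be traced. I claim only that the current texts do not agree.

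Fourth, a reader might infer that the unit is nowhere fixed, or that pooling always changes the chance of success several-fold. Neither holds. The protocol, the SAP criterion sentences and the mock tables all name the subject; one sentence in each SAP conflicts. On the assumed counts, the pooled pass rate with identical routes is 0.97/0.58 = 1.7 times the subject-level rate at 95% and 0.85/0.235 = 3.6 times at 90%. Both ratios shrink once within-subject correlation is allowed for.

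Fifth, the TOST itself treats same-subject data as independent samples. This stands, and the fix has to deal with it.

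**Conclusion.** The point stands. The protocol's trough rule is unsound as written and differs from the rule in both SAPs, on a primary objective. At 20 v 20 the two disagree in 222 of 441 outcomes, always in the direction of Fisher allowing a bridge that the TOST refuses. At the SAPs' own lower margin (90% v 72%), the figures are 80% and 1.6%. These rest on an assumed Fisher level of 0.05, assumed true rates, and independence between routes. The discrepancy over the unit is confined to one sentence per SAP. It matters because pooling counts repeated measures as independent, but the size of its effect depends on counts and correlations that the documents do not give.

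**What to change.** - **Protocol 9.7 and Synopsis:** replace the Fisher rule with the SAPs' Farrington-Manning relative-risk TOST on the proportion of subjects with mean Ctrough at or above 300 ng/mL, margins 0.80-1.25, one-sided 5% on each side. Keep Fisher as descriptive.
- **IM SAP 4.5 and IV push SAP 4.4:** delete the pooling sentence in favour of one mean per subject per route. State that the relative risk refers to the category at or above 300. In the IM SAP, name the deciding mean.
- **Pairing:** state that the same subjects supply both routes, so the independent-samples test is an approximation. Either accept that or pre-specify a paired equivalence version with the same margins.
- **Protocol 9.8:** state that the 80% power inputs concern CL and AUC only and that no power is given for the Ctrough criterion.

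No new data are needed, but the bridge becomes harder to claim. With identical routes and independence, the subject-level TOST passes about 58% of the time at a true 95% and 23% at 90%. With one trough per route and a latent correlation of 0.7 to 0.95, these rise to about 64%-75% and from 31% to 43%-44%. Even 17/20 on both routes fails (p=0.068). If that is unacceptable, a different sample size, margin or paired method should be justified in advance.

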## 9.8 Sample Size and Power Considerations

Considering the large PK variability of Trogarzo® (~70% variability for clearance (CL) based on the population PK model developed for the review of BLA 761065), a minimum subject number of 20 for each type of administration (IVP or IM) is sufficient to achieve 80% power. In addition, the within-subject CV% of AUC with IM (Study TMB-121) and IVI (current TMB-302 preliminary data) administration, are comparable. The median within-subject CV% is 7% for IM and IVI, while the maximum within-subject CV% is 22%-23% for IM and IVI. These data also support that a minimum subject number of 20 for each type of administration is sufficient to achieve 80% power.

